9.2.2 Primary Effectiveness Endpoint

Technical Success defined as *final* residual stenosis ≤50% without flow-limiting dissection (\geq Grade D) of the lesion by angiographic core lab.

Primary Effectiveness will be assessed on a per-lesion basis.

 SHOCKWAVE <small>MEDICAL INC</small>	No.: CP 67398	REV. C
	TITLE: FORWARD PAD IDE Study Protocol	
	CLASS: CLINICAL PROTOCOL	PAGE 36 OF 65

The lower bound for the one-sided 95% Clopper-Pearson exact confidence interval will be reported for the Technical Success rate.

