7.2 Subject Selection

7.2.1 Inclusion Criteria

Subjects are required to meet all of the following inclusion criteria in order to be enrolled in the study. For lesion characteristics, each target lesion must meet eligibility. A maximum of two (2) target lesions may be treated per subject; target lesions may be in the same limb or in different limbs.

General Inclusion Criteria

1. Age of subject is \geq 18 years.
2. Subject is able and willing to comply with all assessments in the study.
3. Subject or subject's legal representative has been informed of the nature of the study, agrees to participate, and has signed the approved consent form.
4. Estimated life expectancy $>$ 1 year.
5. Rutherford Clinical Category 2, 3, 4 or 5 of the target limb(s).

Angiographic Inclusion Criteria

6. One or two target lesion(s) located in a native de novo superficial femoral, popliteal or infrapopliteal artery (above the ankle joint), in one or both limbs.

 SHOCKWAVE <small>MEDICAL INC</small>	No.: CP 67398	REV. C
	TITLE: FORWARD PAD IDE Study Protocol	
	CLASS: CLINICAL PROTOCOL	PAGE 21 OF 65

7. Target lesion reference vessel diameter (RVD) between 2.0 mm and 7.0 mm by investigator visual estimate.
8. Target lesion stenosis $\geq 70\%$ (for vessels below the knee, defined as P3 to the ankle joint) or $\geq 90\%$ (for vessels above the knee) by investigator visual estimate.
9. Target lesion length is ≤ 150 mm by investigator visual estimate. Target lesion can be all or part of the 150 mm treated zone.
10. Calcification is at least moderate defined as presence of fluoroscopic evidence of calcification: 1) on parallel sides of the vessel and 2) extending $> 50\%$ the length of the lesion if lesion is ≥ 50 mm in length; or extending for minimum of 20mm if lesion is < 50 mm in length.

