9.3 Sample Size Determination

The sample size determination for the Mini S Study and FORWARD PAD IDE pooled analysis is based on the Primary Safety Endpoint of MAE at 30 days and the Primary Effectiveness endpoint of Technical Success.

Primary Safety Hypothesis:

$$H_0: \Pi_S > PG_S \text{ vs. } H_A: \Pi_S \leq PG_S$$

where Π_S is the proportion of patients who experience an MAE within 30 days of the index procedure and PG_S is the Safety Performance Goal (PG).

The assumptions for the sample size calculations are listed below.

- Expected 30-day MAE rate of 2.0% = Π_S
- Performance Goal for 30-day MAE of 11.2% = PG_S
- One-sided statistical significance level of 0.025 = α
- The hypothesis will be tested using a one-sided Exact Binomial Test
- Statistical power of 96.5%

Primary Effectiveness Hypothesis:

$$H_0: \Pi_E \leq PG_E \text{ vs. } H_A: \Pi_E > PG_E$$

where Π_E is the proportion of patients with Technical Success and PG_E is the Effectiveness Performance Goal (PG).

The assumptions for the sample size calculations are listed below.

- Expected Technical Success rate of 97.0% = Π_E
- Performance Goal for Technical Success of 85.0% = PG_E
- One-sided statistical significance level of 0.025 = α
- The hypothesis will be tested using a one-sided Exact Binomial Test
- Statistical power of 98.1%

The performance goals are based on previous studies of peripheral IVL and benchmark plaque modification devices. Refer to the statistical analysis plan (SAP) for details.

A one-tailed scenario was used to assess the minimum sample size needed to detect a difference in the assumed true rate of safety (2%) versus the performance safety goal of 11.2%. The same calculation was done for the assumed true rate of effectiveness (97%) versus the performance effectiveness goal of 85%. The sample size of 90 subjects provides a study-wide power of 94.7% to meet both the safety and effectiveness endpoints. The study will be deemed a success if the null hypothesis is rejected for both the primary safety and effectiveness measures. No adjustments for multiplicity are needed.

 SHOCKWAVE <small>MEDICAL INC</small>	No.: CP 67398	REV. C
	TITLE: FORWARD PAD IDE Study Protocol	
	CLASS: CLINICAL PROTOCOL	PAGE 37 OF 65

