2. STUDY OBJECTIVE

The objective of this Clinical Proposal is to use the data that Shockwave Medical is currently collecting from the two clinical studies described above to demonstrate the safety and effectiveness of the Shockwave Medical JAVELIN Peripheral IVL Catheter compared to pre-defined performance goals. This document may modify and supersede the statistical plans outlined in the respective study protocols.

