6.2. Primary Effectiveness Hypothesis

The primary effectiveness hypothesis is:

$$H_0: \Pi_E \leq PG_E \quad \text{vs.} \quad H_A: \Pi_E > PG_E$$

where Π_E is the proportion of target lesions with technical success and PG is the effectiveness Performance Goal.

The assumptions for the sample size calculations are listed below.

- Expected Technical Success rate of 97.0% = Π_E
- Performance goal of 85.0% = PG_E
- One-sided statistical significance level of 0.025 = α
- The hypothesis will be tested using a one-sided Exact Binomial Test.
- Statistical power of 98.1%.

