6.3. Sample Size Justification

The study will be deemed a success if both the primary safety and effectiveness endpoints are met. To provide at least 80% power study-wide, each endpoint was powered to at least 90%. A one-tailed scenario was used to assess the minimum sample size needed to detect a difference in the assumed true rate of safety (2%) versus the safety performance goal of 11.2%. The same calculation was done for the assumed true rate of effectiveness (97%) versus the performance effectiveness goal of 85%. A sample size of 90 subjects provides a study-wide power of 94.7% to meet both the safety and effectiveness endpoints. No adjustments for multiplicity are needed.

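### Technical Success is tested per lesion with a plain exact binomial although a subject may contribute two lesions, so the one-sided 0.025 level is not guaranteed and the stated power and pass threshold belong to 90 single units

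*Protocol*

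**What the plan says.** The unit of the primary effectiveness analysis differs between sections:

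- Protocol 9.2.2: "Primary Effectiveness will be assessed on a per-lesion basis".
- Protocol 9.3: the parameter in the effectiveness hypothesis "is the proportion of patients with Technical Success".
- SAP 6.2: the same parameter "is the proportion of target lesions with technical success".

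SAP section 2 adds: "This document may modify and supersede the statistical plans outlined in the respective study protocols". The lesion is therefore the more likely governing unit.

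Protocol 7.2.1 allows at most two target lesions per subject, and "target lesions may be in the same limb or in different limbs". Protocol 7.7 treats them within the index procedure.

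On method, SAP 6.2 says "The hypothesis will be tested using a one-sided Exact Binomial Test", at one-sided 0.025 against a performance goal of 85.0%. Protocol 9.2.2 adds an interval: "The lower bound for the one-sided 95% Clopper-Pearson exact confidence interval will be reported for the Technical Success rate".

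Sample size is stated only in subjects. SAP 6.3: "A sample size of 90 subjects provides a study-wide power of 94.7% to meet both the safety and effectiveness endpoints". The effectiveness component is given as 98.1% power at a true rate of 97.0%. The Meta-Analysis Discussion in SAP Appendix B says that rejection with 90 subjects corresponds to success rates from 93.3% upwards.

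Neither document gives an expected number of lesions, a within-subject correlation, a cluster adjustment, or a rule for reducing two lesions to one result per subject.

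**The concern.** The exact binomial test and the Clopper-Pearson bound both assume independent units. Two lesions in one subject share the patient, usually the operator and the session, and probably much of the calcium burden. Positive correlation is plausible, although its size is unknown. With positive correlation the number of failures varies more than the binomial allows. The lesion-level bound is then too narrow, and a device with true success of 85% passes more often than the binomial calculation says.

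Technical Success is one of two endpoints that must both be met, and the result supports a 510(k) submission, so its nominal level should hold whatever mix of one- and two-lesion subjects is enrolled. A second problem needs no assumption about correlation. Once any subject has two lesions, the test has more than 90 units and a different cut-off, so the published power and threshold no longer describe it.

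**Working it through.** **Inputs from the documents.** 90 subjects; one or two lesions each; performance goal 85%, so failure probability 0.15 under the null; expected success 97%, so failure probability 0.03; one-sided level 0.025; exact binomial test.

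**Assumed, because the documents do not give them.** k, the number of subjects with two lesions, and rho, the within-subject correlation of lesion failure.

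**Step 1: reproduce the plan's figures.** The test passes when failures are at most c, the largest c with P(Bin(L, 0.15) ≤ c) ≤ 0.025. For L = 90, c = 6, so at least 84/90 = 93.3% must succeed.

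- Actual level: P(Bin(90, 0.15) ≤ 6) = 0.0131.
- Power: P(Bin(90, 0.03) ≤ 6) = 0.981, the stated 98.1%.
- Safety: at most 4 events in 90 gives level 0.0218 and power 0.965.
- Joint: 0.965 × 0.981 = 0.947, the stated 94.7%.

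All the stated figures are therefore for 90 independent single units.

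**Step 2: the lesion-level test.** With k two-lesion subjects there are L = 90 + k lesions. The planned test takes its cut-off from Bin(L, 0.15). The true distribution of failures is the convolution of 90 − k single lesions with k pairs, where P(both fail) = p² + rho·p(1 − p). True one-sided error at p = 0.15:

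| k | L | Pass at | rho 0 | rho 0.1 | rho 0.3 | rho 0.5 |
|---|---|---|---|---|---|---|
| 0 | 90 | 84 (93.3%) | 0.0131 | – | – | – |
| 10 | 100 | 93 (93.0%) | 0.0122 | 0.0128 | 0.0142 | 0.0156 |
| 20 | 110 | 101 (91.8%) | 0.0244 | 0.0264 | 0.0305 | 0.0348 |
| 25 | 115 | 106 (92.2%) | 0.0159 | 0.0176 | 0.0214 | 0.0256 |
| 30 | 120 | 110 (91.7%) | 0.0217 | 0.0242 | 0.0296 | 0.0353 |
| 45 | 135 | 124 (91.9%) | 0.0127 | 0.0151 | 0.0204 | 0.0264 |
| 90 | 180 | 163 (90.6%) | 0.0192 | 0.0240 | 0.0347 | 0.0461 |

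The error does not rise steadily with k, because the discreteness of the test leaves a different amount of slack at each L.

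**Step 3: how often 0.025 is exceeded.**

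| Range of k | rho 0.1 | rho 0.3 | rho 0.5 |
|---|---|---|---|
| 20-30 (11 counts): number above 2.5% | 2 | 5 | 8 |
| 20-30: range of error | 1.4-2.6% | 1.7-3.2% | 2.1-3.7% |
| 1-45 (45 counts): number above 2.5% | 4 | 13 | 26 |
| 1-45: average error | 1.9% | 2.2% | 2.6% |

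Over all k from 0 to 90 the maximum is 4.1% at rho 0.3 and 5.3% at rho 0.5, both at k = 87.

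**Step 4: power and threshold.** At 97% lesion success, the planned test's power is at least 97.6% for every k from 0 to 90, even at rho = 1. For k = 20-30 it is 99.3-99.9% (rho 0 to 0.5). The pass threshold for k = 20-30 is 91.6-92.4% of lesions, not 93.3%.

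**The case against.** The strongest reply is about size. Nothing in the documents points to 20-30 two-lesion subjects. The only lesions-per-patient figure is in Protocol 3.1.2: an earlier below-the-knee cohort with 114 arteries in 101 patients. If every extra artery is a second lesion, 13/101 × 90 gives about 12 two-lesion subjects here. For k = 1-19 the error never exceeds 2.5% at rho 0.1, exceeds it at one count at rho 0.3 (k = 12, 2.68%), and at four counts at rho 0.5 (maximum 2.94%). The figures of 4.1% and 5.3% need almost every subject to have two lesions.

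This stands as a limit on the size: the excess may be small or absent. It does not restore the guarantee. Control then depends on a count that nobody has fixed. At rho 0.5 the error is 1.5% with 11 two-lesion subjects and 2.9% with 12.

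Three other points are fair:

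- The 93.3% in Appendix B is explanatory and is not the decision rule, and the stated power is generally conservative. The mismatch of units therefore misdescribes the test but does not by itself cause a wrong decision.
- The reported Clopper-Pearson bound is one-sided 95%, so it does not decide success; the 0.025 test does. Both rest on the same independence assumption.
- SAP section 2 is permissive (may supersede), and SAP 5.2 and 6.3 still count subjects. The unit should be reconciled explicitly and not left to inference.

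**Conclusion.** The point holds. The governing reading is a lesion-level test that treats possibly paired lesions as independent, so its one-sided 0.025 level is not guaranteed. The likely excess is modest: the error reaches at most 3.7% with 20-30 two-lesion subjects and correlation up to 0.5, and stays at 1.3-1.6% with 10 (correlation 0.1 to 0.5). These sizes rest on assumed values of k and rho. The omission itself, the conflict between Protocol 9.3 and the other two sections, and the fact that 98.1% and 93.3% describe 90 single units rest on no assumption. There is no material loss of power. The change should be made, and before the data are analysed, because choosing a unit or adjustment after seeing results would weaken the claim.

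**What to change.** 1. **One unit.** Use the same unit in Protocol 9.2.2, Protocol 9.3 and SAP 6.2. Keeping the SAP's lesion unit is reasonable.

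2. **A primary test and bound that allow for two lesions per subject.** One option divides failures and N by the design effect D = 1 + rho·(Σm²/L − 1), where m is lesions per subject, and then applies the Clopper-Pearson formula. For k = 20, Σm² = 70 + 4 × 20 = 150, L = 110, and with rho = 0.5, D = 1 + 0.5 × (150/110 − 1) = 1.18, an effective N of about 93. The divided counts are not integers, so the method is approximate. Checked against the exact distribution with rho fixed at 0.5, its maximum error is 2.35% over k = 1-90 and true correlation 0 to 0.5. Control is not shown for higher correlation.

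3. **Fix rho in advance.** At 97% success only about 3-4 failures are expected (0.03 × 110 = 3.3; 0.03 × 120 = 3.6), too few to estimate it. The value 0.5 is a choice the sponsor should justify. A cluster-robust bound is an alternative but is fragile with so few failures.

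4. **Restate.** Give the assumed number of lesions and rho, the resulting power and joint power, and the Appendix B threshold.

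5. **Sensitivity analysis.** Add a per-subject analysis in which success requires all target lesions to succeed. If the sponsor prefers it as primary, it changes the estimand. At 97% lesion success and correlation 0 to 0.5, its power is 94.0-97.1% when 20-30% of subjects have two lesions and 89.4-94.9% when half do.

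**Cost.** Wording in both documents; no new data or subjects. With rho fixed at 0.5 and 20-30 two-lesion subjects, the adjusted test allows 0 or 1 fewer lesion failure, and power is 98.3-99.7% instead of 99.3-99.9%.

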6.2 Number of Subjects

Up to 75 subjects treated with moderate to severely calcified peripheral artery disease (PAD) with a target lesion located in a native, *de novo* superficial femoral, popliteal or infrapopliteal artery will be enrolled. A minimum of 15 BTK lesions are required and up to two (2) target lesions may be treated per subject.

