9.2 Primary Endpoints

9.2.1 Primary Safety Endpoint

Major Adverse Events (MAE) at 30 days defined as a composite of:

- All-cause death
- Clinically-driven target limb revascularization (CD-TLR)
- Unplanned target limb major amputation (above the ankle)

SAEs will be reviewed and adjudicated by the CEC. Only those adjudicated as MAEs will comprise the composite safety endpoint.

MAEs will be assessed on a per-subject basis.

The upper bound for the one-sided 95% Clopper-Pearson exact confidence interval will be reported for the MAE rate.

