5.1. Performance Goal for Safety

As noted in Section 4.1, the primary safety endpoint for the pooled analysis cohort is MAE at 30 days. This is consistent with the pooled PAD I & II analysis and the Disrupt PAD BTK study, previously submitted to FDA in K161384 and K180454, respectively. MAE is a clinically relevant composite endpoint frequently used in peripheral vascular research [1-4]. Composites generated by the combination of individual endpoints provide additional statistical power to detect potentially meaningful differences between treatments [5].

In the pooled PAD I/II analysis, the PG for 30-day MAE was 8.7%. For the pooled primary safety hypothesis, a conservative 2.5% non-inferiority adjustment was applied to account for a more complex patient population in the JAVELIN studies including Rutherford Classification 5, dialysis patients, smaller diameter vessels, infrapopliteal lesions, and a higher rate of chronic total occlusions (CTOs). As a result, the primary safety endpoint PG for 30-day MAE is 11.2%.

The primary safety endpoint PG is further supported by the clinical literature for benchmark plaque-modifying devices designed to treat PAD. The literature review -described above identified 16 unique sources with at least 50 subjects and published within the last 10 years, representing 3,207 subjects, with complete data available for 30-day MAE (see Appendix B for details). Sample sizes ranged from 50 to 800, and the reported 30-day MAE rates ranged from 0.0% - 14.0% with associated 95% upper confidence limits ranging from 2.2 - 22.3%. The meta-analysis random effects model estimated a mean 30-day MAE rate of 2.8% (95% CI: 1.6-4.9).

As noted in Section 6.1 below, with a PG of 11.2% and 90 subjects, rejection of the null hypothesis would demonstrate an expected true population 30-Day MAE rate of 2.0% with an upper 2-sided 95% CI of less than or equal to 11.2% which are clinically and regulatory appropriate estimates based on prior investigations of peripheral IVL [1-3] and also consistent with the broader contemporary peripheral literature sources and meta-analysis (Appendix B).

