As noted in Section 6.2 below, with a PG of 85.0% and 90 subjects, rejection of the null hypothesis would demonstrate an expected true population rate of 97.0% with a lower 2-sided 95% CI of greater than or equal to 85% which are a clinically and regulatory appropriate estimates based on prior investigations of peripheral IVL [1-3] and -also consistent with the broader contemporary peripheral literature sources and meta-analysis. (Appendix B).

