The literature review identified 9 unique sources, representing 2129 total subjects, that reported the percentage of cases with final residual stenosis <50% (see **Figure B2**). Sample sizes ranged from 52 to 733, and the reported rates ranged from 83.2% - 100%. In the meta-analysis, the common effects model estimated final residual stenosis <50% at 89.0% (95% CI: 87.5-90.4), and the random effects model estimated a rate of 92.5% (95% CI: 88.5-95.2). Residual heterogeneity was considered high with $I^2 = 80\%$.

Figure B2. Forest Plot for Final Residual Stenosis < 50%

Meta-Analysis Discussion

Substantial residual heterogeneity was observed in both analyses, represented by I^2 values greater than 70% and p-values associated with the I^2 of <0.01 . The I^2 value represents the percentage of all observed heterogeneity that is attributed to between-study variance in the true population proportion, and a significant p-value indicates that the null hypothesis of a single true population proportion (Π) has been rejected, and thus the point estimate represents a range of true population proportions. A high I^2 value indicates that, while the point estimate of the range of true population proportions is accurate, it will be less precise than is optimal for a performance goal that will be applied across a range of studies. The study hypotheses take these findings into consideration.

With a PG of 11.2% and 90 subjects, rejection of the null hypothesis would demonstrate an expected true population 30-Day MAE rate of 0.0-4.4% with an upper 2-sided 95% CI of less than or equal to 11.2% and with a PG of 85.0%. Rejection of the null effectiveness hypothesis would demonstrate an expected true population rate of 93.3 - 100.0% with a lower 2-sided 95% CI of greater than or equal to 85%. These results are clinically and regulatory appropriate estimates based on prior investigations of peripheral IVL [1-3] and are also consistent with the broader contemporary peripheral literature sources and meta-analysis.

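### The protocol reports one-sided 95% exact bounds for primary endpoints tested at one-sided 0.025, so a reported bound can clear its goal when the test fails

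*Protocol*

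**What the plan says.** Protocol 9.2.1 and 9.2.2 are the only places that instruct which bound to report for the primary endpoints. For safety: "The upper bound for the one-sided 95% Clopper-Pearson exact confidence interval will be reported for the MAE rate". For effectiveness: "The lower bound for the one-sided 95% Clopper-Pearson exact confidence interval will be reported for the Technical Success rate".

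Protocol 9.3 sets the test for each endpoint as a one-sided exact binomial test, with "One-sided statistical significance level of 0.025". SAP 6.1 and 6.2 repeat this. Success depends on the tests alone: "The study will be deemed a success if the null hypothesis is rejected for both the primary safety and effectiveness measures".

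Where the SAP describes what rejection would show, it uses a different interval from Protocol 9.2. SAP 5.1 links rejection to an MAE rate "with an upper 2-sided 95% CI of less than or equal to 11.2" percent. SAP 5.2 links it to a success rate "with a lower 2-sided 95% CI of greater than or equal to 85" percent. The discussion in SAP Appendix B does the same and gives the passing range of success rates: "expected true population rate of 93.3 - 100.0% with a lower 2-sided 95% CI of greater than or equal to 85" percent.

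**The concern.** An exact one-sided 95% bound clears a goal when the one-sided exact p-value is below 0.05. The trial needs p at or below 0.025, which corresponds to a one-sided 97.5% bound, that is, one limit of the two-sided 95% interval. The documents thus pair the same two goals with two confidence levels, and the reporting instruction carries the looser one.

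In a single-arm study against performance goals, the natural reading of a result is to set the bound beside the goal. As written, a result that fails its pre-specified test can be shown with a pre-specified bound on the passing side of the goal. That invites a dispute over which one governs. Even when the two agree, each bound looks tighter than the test level supports.

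**Working it through.** **Inputs.** Goals 11.2% (MAE) and 85.0% (Technical Success), expected rates 2.0% and 97.0%, n = 90, alpha 0.025 one-sided, stated powers 96.5%, 98.1% and 94.7% jointly: all from Protocol 9.3. Bound level, one-sided 95%: Protocol 9.2.1 and 9.2.2.

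**1. Which level produced the plan's figures.** Let F be the number of effectiveness failures and X the number of MAEs, both binomial with n = 90.

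- Effectiveness: P(F ≤ 6 | 0.15) = 0.0131 and P(F ≤ 7 | 0.15) = 0.0308. At 0.025 the test allows at most 6 failures, so at least 84/90 = 93.3%. Power P(F ≤ 6 | 0.03) = 98.1%.
- Safety: P(X ≤ 4 | 0.112) = 0.0218 and P(X ≤ 5 | 0.112) = 0.0537. The test allows at most 4/90 = 4.4%. Power P(X ≤ 4 | 0.02) = 96.5%.
- Joint power: 0.9652 × 0.9812 = 0.947.

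All three stated powers reproduce. At 0.05 the effectiveness test would allow 7 failures and its power would be 99.4%, not 98.1%. The cut-offs 93.3% and 4.4% are also the ends of the ranges in SAP Appendix B. So 0.025 is the intended level, and the reporting sentences are the outliers.

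**2. Bound against test for effectiveness.** The Clopper-Pearson lower bound for x successes in n, at one-sided confidence 1 − a, is the a-quantile of Beta(x, n − x + 1).

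| Result | Exact p | Reported bound (a = 0.05) | Matched bound (a = 0.025) | Test at 0.025 |
|---|---|---|---|---|
| 83/90 | 0.0308 | 85.9% | 84.6% | fails |
| 84/90 | 0.0131 | 87.3% | 86.1% | passes |
| 92/100 | 0.0275 | 86.0% | 84.8% | fails |

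At 83/90 and at 92/100 the reported bound is above 85.0% although the test fails. The matched bound agrees with the test in every row.

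The probability of exactly 83/90 is 1.3% at a true rate of 97%, 8.3% at 95% and 14.9% at 93%. Only 97% is a design assumption; the other two show the sensitivity. For context, the literature estimate in SAP 5.2 is 92.5%.

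**3. Other lesion counts.** Effectiveness is assessed per lesion (Protocol 9.2.2), and "up to two (2) target lesions may be treated per subject". The documents give no expected lesion count, so I assumed 80 to 180. Over those 101 counts, the failures allowed at 0.05 exceed those allowed at 0.025 by one at 84 counts and by two at 16. They agree only at n = 84. This says that a conflicting result exists at nearly every count, not that it is likely: at a true rate of 97% its probability is 0.7% at n = 100 and below 0.1% at n = 120.

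**4. Bound against test for safety.** The upper bound for x events is the (1 − a)-quantile of Beta(x + 1, n − x).

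| Result | Exact p | Reported bound (a = 0.05) | Matched bound (a = 0.025) | Test at 0.025 |
|---|---|---|---|---|
| 4/90 | 0.0218 | 9.9% | 11.0% | passes |
| 5/90 | 0.0537 | 11.3% | 12.5% | fails |
| 4/88 | 0.0255 | 10.1% | 11.23% | fails |

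At n = 89 to 91 both levels allow at most 4 MAEs, so there is no conflict. At every n from 80 to 88, exactly 4 MAEs clears the goal on the reported bound and fails the test. SAP 9.3 counts only subjects with at least 23 days of follow-up or an earlier event, so a denominator below 90 is possible. There is also one conflicting count at each n from 92 to 100, but a 90-subject primary cohort cannot reach those.

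**The case against.** The strongest reply is that nothing turns on the bound. Protocol 9.3 decides success by the tests, the bound is labelled openly, and it is valid at its stated level; a reader would have to ignore both the label and the test result to be misled. The first part stands: the success decision, the type I error and the power do not change. It does not remove the mismatch between the interval and the test of the same primary endpoint.

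A second reply is that SAP section 2 says the SAP may modify and supersede the protocol's statistical plan, and that the SAP speaks of two-sided 95% limits. But that wording sits in the rationale for the goals. The SAP neither withdraws nor replaces the reporting instruction.

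A third is that safety is scarcely affected. The SAP describes the cohort as the first 90 evaluable subjects, which may hold the denominator at 90, where the levels agree. This largely stands. The safety conflict needs at least two of the 90 to drop out of the denominator, and the 88-subject example misses only narrowly.

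Last, the unit of the effectiveness analysis is not wholly settled: Protocol 9.3 defines the proportion over patients, whereas Protocol 9.2.2 and SAP 6.2 use lesions. The 83/90 example does not depend on this, since the sample size calculation itself uses 90.

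**Conclusion.** The concern holds. The reported bounds for both primary endpoints are set at a level that does not match the test. For effectiveness the conflict occurs at the planned n of 90 (83 successes) and at 100 of the 101 lesion counts in the assumed range of 80 to 180. For safety it does not occur at 89 to 91 subjects, but it does at each denominator from 80 to 88, a range that is also assumed. The consequence is a misleading or contradictory report, not a wrong decision rule. It should be fixed before results are known.

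**What to change.** In Protocol 9.2.1 and 9.2.2, change the level of the Clopper-Pearson bound from one-sided 95% to one-sided 97.5% (two-sided 95%). Bound and test then agree at every n, and the protocol matches the interval already used in SAP 5.1, 5.2 and Appendix B. Goals, tests, sample size and power stay as they are.

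The cost is a few words in two sections, and bounds about one point closer to the goal: at 87/90 successes the lower bound goes from 91.6% to 90.6%, and at 2/90 MAEs the upper bound goes from 6.8% to 7.8%.

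A separate, minor drafting point in SAP 5.2 could be explained in one sentence at the same time. It takes 89.3% with a 5% adjustment to 85.0%, but 89.3 − 5 = 84.3 and 89.3 × 0.95 = 84.8. The 85.0% goal is stricter than either and remains the tested goal.
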